- Case finding of individuals with increased risk of a fall injury. In the start of the intervention this was primarily done within the boroughs through physiotherapists and occupational therapists who looked for patients with increased risk of falling in their clinical practices. Education on fall risks and possible follow-up was also given to the General Practitioners (GPs) and at the community centers for case finding. From September 2017 the Injury Clinic at Oslo University Hospital started sending so-called "fall reports" to the boroughs when 65+ patients with fall related injuries had been treated at the clinic, assisting the boroughs in identifying cases and targeting this high-risk population in their preventive initiatives.
- Shared, collaborative single point of entry to care in the boroughs. This is the address to where the fall reports from the Injury Clinic were sent. The same address was conveyed to the GPs and the other health professionals to send messages whenever a need for falls risk assessment and intervention was detected. On the receiving end of this address, is a care coordinator with extensive knowledge about the local health care system and the fall prevention pathway who forwards the messages to launch the right follow-up.
- A cross-sectoral plan for follow-up with role clarification. This was a major part of improving the coordination of care. Who identifies the elderly at risk of fall injuries and how (case finding)? Who performs the fall risk assessments? What measures are taken to reduce risk, who delivers these interventions and how are the at-risk-patients recruited into the follow-up? Both the leadership and those who delivered the services within the boroughs were included in the planning process. The cross-sectoral plans were developed both separately within the two boroughs and some parts in coordination with the Injury

Clinic, specialists at the University Hospital and the Department of Public Health of the Municipality of Oslo.

- Interdisciplinary teams were established in the two boroughs, consisting of those who did fall risk assessments through home visits. The teams consisted mainly of physiotherapists and occupational therapists. Nurses, nutritionists, and clinical pharmacologist were added later. These teams received referrals for risk assessments from the single point of entry, sent from the Injury Clinic as fall reports and as well messages from by other health professionals within the boroughs.

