- The main technology enabler in this intervention, was the digitalization in 2018 of the home visit assessment tool in the Electronic Patient Records (EPR) for the boroughs. In addition, a way of registering falls in the same EPR as well as a clear routine for how to document the multifactorial assessment and the follow up within this system, was a great support for those who did the home assessments and follow-up interventions. Digitalization of the fall reports in 2018 from the Injury Clinic, also was an improvement.

Timeline

Improving care coordination is a process. The investigators have, however, chosen to define these dates as the start of intervention, as this was the time when the systematic needs assessment together with the interdisciplinary and cross-sectoral approach to the fall-risk-prevention-problem, started.

These were the milestones which were chosen as start dates of the intervention:

1. Start of intervention in Nordstrand borough is set to January 1, 2015.

The Chief Medical Officer in Nordstrand mobilized the health professionals in a systematic needs assessment. They improved case finding, developed a checklist for multifactorial falls risk assessment through home visits, recruited more elderly at risk into exercise programs, and started education of health professionals including the GPs in coordination with the geriatricians at the University Hospital and local nursing homes. They also improved primary prevention with winter road safety measures and education of the general elderly population on fall risks and safety measures.

After Østensjø and the Injury Clinic at Oslo University Hospital joined the intervention in September 2016, the intervention in Nordstrand was done in collaboration and coordinated with these partners.

2. Start of intervention in Østensjø borough is set to September 1, 2016.

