Fall injury will be included as a time-varying exposure variable. The individuals in the cohort are all registered as non-fallers until they are registered with a new fall injury in the NPR database, when they shift status to fallers.

Exposure categories

• Fallers in the intervention boroughs

Fallers 65+ years from the borough of Nordstrand from January 1. 2015 Fallers 65+ years from the borough of Østensjø from September 1. 2016

• Fallers in the control boroughs

Fallers 65+ years from all the 13 other boroughs of Oslo.

Non-fallers

All non-fallers from the complete Oslo population 65+ years.

Main analysis: In the main analysis (2015-2019), fallers from the two intervention boroughs, Nordstrand (from January 2015) and Østensjø (from September 2016), will be compared with fallers from the control boroughs during the intervention. In addition, the two categories of fallers will also be compared with the non-fallers. A similar analysis will be performed before the intervention started using data from 2012-2013. Any differences between the intervention and control boroughs before the intervention started will be taken into account.

In a secondary analysis, the total incidence (not restricted to fallers) of hip fracture in the intervention boroughs will be compared with the incidence of hip fracture in the control boroughs, and a similar comparison will be made before the intervention started. Adjustment for possible time trends will be considered.

Primary outcome variables

- Hip fracture
- Admittance to nursing home, long term
- Death (all-cause mortality)

Secondary outcome variables

Other fall injuries

In each analysis, participants with a hip fracture or living in a nursing home at baseline will be excluded.

Statistical power

According to statistics from NPR before the intervention started, around 22% of the home dwelling elderly treated for a fall injury came from the intervention boroughs of Nordstrand and Østensjø.

If 22% of the patients with falls are exposed to the fall prevention intervention and 607 of all fallers suffer a hip fracture during a follow-up of five years (2015-2019), it will enable us to detect a relative risk reduction of 24% (RR= 0.76) at the 0.05 significance level with a power of 80%.

Data management and analysis

The Cohort Data is stored at Services for Sensitive Data (TSD) at the University of Oslo.

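### The single city-wide non-faller reference is partly exposed to the intervention and mixes borough groups, which affects the additional faller-versus-non-faller hazard ratios but not the main contrast

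*Combined protocol and SAP*

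**What the plan says.** Under Exposure categories, the combined protocol and SAP splits fallers by borough group, with start dates of January 1, 2015 for Nordstrand and September 1, 2016 for Østensjø. Non-fallers are not split: the category is "All non-fallers from the complete Oslo population 65+ years". Membership depends on a registry event alone, since participants are "all registered as non-fallers until they are registered with a new fall injury in the NPR database".

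Under Main analysis, intervention-borough fallers "will be compared with fallers from the control boroughs during the intervention". The plan continues: "In addition, the two categories of fallers will also be compared with the non-fallers". On the earlier period it says "A similar analysis will be performed before the intervention started using data from 2012-2013" and "Any differences between the intervention and control boroughs before the intervention started will be taken into account". It states no method for this.

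Two parts of the intervention description concern people who need not have a registered fall injury. The case-finding step relied at first on "physiotherapists and occupational therapists who looked for patients with increased risk of falling in their clinical practices". For Nordstrand, Timeline item 1 adds: "They also improved primary prevention with winter road safety measures and education of the general elderly population on fall risks and safety measures".

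**The concern.** A hazard ratio for fallers against non-fallers will usually be read as the excess risk that follows a fall injury. Here each of the two ratios carries more than that. The reference contains intervention-borough residents who may have been reached by the programme before any registered injury. It also contains residents of boroughs other than those of the fallers being compared. If the programme lowers risk in people who have not yet had a registered injury, that benefit lowers the reference hazard and appears as a higher ratio for fallers, including fallers in the control boroughs.

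Two things are at stake. One is the interpretation of results that the plan places within its main analysis, for hip fracture, long-term nursing home admission and death. The other is a missed comparison: no planned analysis sets intervention-borough non-fallers against control-borough non-fallers. That comparison would show a primary-prevention effect or a borough trend unrelated to the programme, and either would bear on how the main result is read.

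**Working it through.** **1. The plan's own figure.** The Statistical power section gives 607 hip fractures among fallers, 22% exposed, RR 0.76, significance level 0.05 and power 80%. By Schoenfeld's formula, two-sided:

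events = (1.960 + 0.842)² / [0.22 × 0.78 × (ln 0.76)²] = 7.849 / (0.1716 × 0.0753) ≈ 608, and 607 events give power 0.7998.

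The figure reproduces. It concerns fallers against fallers only.

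**2. Set-up.** Assume constant hazards and set the control-borough non-faller hazard to 1. Let
- F = hazard ratio for a fall injury;
- T = intervention effect in fallers;
- t = intervention effect in non-fallers;
- b = pre-existing hazard ratio, intervention to control boroughs;
- w = exposed share of non-faller person-time.

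The pooled reference hazard is R = (1 − w) + w·b·t. Then
- intervention fallers against the pooled reference: F·b·T / R;
- control fallers against the pooled reference: F / R;
- ratio of the two: b·T, in which R does not appear.

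So the faller-versus-faller contrast does not depend on how non-fallers are pooled.

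**3. Partly exposed reference.** The documents give no value for w, b or t. As assumptions, take w = 0.22 (borrowed from the share of fallers), b = 1, and t from 0.76 (the plan's detectable effect in fallers) to 0.90. Both faller ratios are multiplied by 1/R compared with an unexposed reference:
- t = 0.76: R = 0.78 + 0.22 × 0.76 = 0.947, and 1/R = 1.056;
- t = 0.90: R = 0.78 + 0.22 × 0.90 = 0.978, and 1/R = 1.022.

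Østensjø was not exposed for the first 20 of the 60 months of 2015–2019. With an assumed equal split between the two boroughs, w = 0.11 + 0.11 × 40/60 = 0.183:
- t = 0.76: R = 1 − 0.183 × 0.24 = 0.956, and 1/R = 1.046;
- t = 0.90: R = 1 − 0.183 × 0.10 = 0.982, and 1/R = 1.019.

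The range is about 2–6%.

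**4. Mixed boroughs.** With w = 0.22, b = 1.10 and no effect in non-fallers (t = 1), R = 0.78 + 0.22 × 1.10 = 1.022. Against non-fallers of the same borough group, the intervention-faller ratio is multiplied by 1.10/1.022 = 1.076 and the control-faller ratio by 1/1.022 = 0.978.

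**5. What the 2012–2013 analysis can remove.** Divide the 2015–2019 ratio by the 2012–2013 ratio for the same group, with F and b stable. Before the intervention, t = T = 1.
- With t = 1 in the later period too, b cancels completely.
- With b = 1.10 and t = 0.76, R is 1.022 before and 0.78 + 0.22 × 1.10 × 0.76 = 0.964 after. Both before/after ratios are then raised by 1.022/0.964 = 1.060.

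The stable borough difference is removed almost entirely. The effect in non-fallers is not.

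**The case against.** The strongest reply is that the effect estimate of interest is the faller-versus-faller contrast, which is untouched. The non-faller comparisons are introduced as additional, and a common benchmark for both faller groups is a legitimate choice. The plan does not say that these ratios will be read as borough-specific excess risk after a fall. This stands, and it limits the weight of the point.

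The plan also has a 2012–2013 analysis and promises to account for earlier differences. That can deal with a stable borough difference, so the example in step 4 should not be read as a bias left in the final results. It cannot deal with an effect that begins with the intervention.

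A reader might infer that any effect in people without a registered injury is hidden altogether. The documents do not support that. The secondary analysis compares total hip fracture incidence between borough groups, not restricted to fallers, with a similar earlier comparison. It would partly capture such an effect, but only for hip fracture and only with fallers and non-fallers combined.

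A reader might also infer that non-fallers of the same boroughs are the natural cure. On the premise of this point, that makes the intervention-borough reference wholly exposed after the start date. Compared with an unexposed reference, the intervention-faller ratio would then be raised by 1/0.90 to 1/0.76, or 11–32%. The ratio of the two faller hazard ratios would also no longer equal the faller-versus-faller contrast.

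Finally, the assumed effects may be generous. An HR of 0.76 is the detectable effect among fallers, applied here to every exposed non-faller. Measures for the general elderly population are described only for Nordstrand.

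**Conclusion.** The point holds for the two additional faller-versus-non-faller comparisons. Their reference is partly exposed and mixes borough groups, so neither ratio is a clean measure of excess risk after a fall injury. It would be wrong to infer that the main effect estimate or the 80% power is compromised: the reference cancels from that contrast.

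The size rests wholly on assumptions. An exposed share of 18–22% and a hazard ratio of 0.76–0.90 in non-fallers put both faller ratios about 2–6% above their values against an unexposed reference. With no effect in non-fallers and equal baseline hazards, the distortion is nil. The change is worth making because it costs little and adds a comparison among non-fallers that the plan lacks.

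**What to change.** Code four time-varying categories: faller or non-faller, by intervention or control borough, using the stated start dates. Østensjø residents before September 2016 should be handled in the same way whether or not they have fallen. Use control-borough non-fallers as the common reference. They are outside the two intervention boroughs, and the ratio of the two faller hazard ratios then still equals the faller-versus-faller contrast.

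From the same model, report intervention versus control among non-fallers in 2012–2013 and in 2015–2019 for all three primary outcomes, as a check for a primary-prevention effect or an unrelated borough trend. This reference does not itself remove a pre-existing borough difference: the intervention-faller ratio carries b in full. Division by its 2012–2013 counterpart gives F·b·T / (F·b) = T when F and b are stable, so the before/after step should be written into the plan.

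Same-borough faller-versus-non-faller ratios may be added as descriptive results, with a note that intervention-borough non-fallers are themselves exposed.

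The cost is one recoded variable in existing data and a somewhat smaller reference group: about 78% of non-faller person-time if the 22% assumption holds.

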Study Protocol and Statistical Analysis Plan

Does the Improved Coordination of Care for Fall- and Fracture Prevention in Oslo Have Effect on the Rate of Hip Fractures, Need of Nursing Homes or Death?

RCN296587

January 2. 2023

The study is an evaluation of a new patient follow-up for fall- and fracture prevention in the municipality of Oslo with improvement of coordination of care for elderly (65 years or older, 65+) at risk of fall injuries.

The two major innovations in this initiative are 1) the systematic approach to improving care coordination within the health care system as well as 2) including osteoporosis evaluation in the fall risk assessment in order to reduce risk of fall related fractures.

In this study, the two city boroughs of Nordstrand and Østensjø, who initiated the intervention, are compared with a control group consisting of the other 13 city boroughs of Oslo in a controlled before and after study design.

The care coordination implemented is in line of the framework Øvretveit used in his summary review "Does clinical coordination improve quality and save money?" (2011)ⁱ, and which WHO later adopted in their practice brief "Continuity and coordination of care" (2018)ⁱⁱ. The major steps in the intervention in Oslo are as follows:

- Needs assessment and user involvement. The intervention started with the chief medical officers in the areas of intervention realizing the health burden of hip fractures within their boroughs, as well as the lack of care coordination in the delivery of preventive measures. The steps of the intervention were developed as a cooperative effort with the local health professionals who delivered the services, the chief medical officers in the boroughs and specialists in geriatrics, osteoporosis and injuries at Oslo University Hospital.

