Østensjø started a collaboration with Nordstrand borough and the Injury Clinic in September 2016 after a grant proposal ("Samhandlingsmidler") was awarded funding. This led to a development of a formal multifactorial falls and fracture risk assessment tool for GPs, a revision of the interdisciplinary falls risk assessment tool from Nordstrand for home visits, establishing referral pathways within primary care and with specialist care established. In addition, education programs for both GPs and other health professionals in primary care was strengthened. Local champions were chosen and interdisciplinary working groups were established.

3. The Injury Clinic supported case finding from September 2017

All municipalities started receiving **fall reports** regarding consenting patients with fall injuries treated at the Injury Clinic at the University Hospital in Oslo from September 2017. This improved the case finding in both Nordstrand and Østensjø, who already had a coordinated care plan in place, which were presumed to be the crucial part of the intervention. The 13 other municipalities did not have the same coordinated care. Their patients received care as usual, which varied between the boroughs.

4. The end of the study period is set to December 31. 2019

The intervention in Oslo expanded to include most of the city boroughs after 2019. From January 2020 five more boroughs started care coordination, another five during 2021 and further one in 2022. The end of the study period with comparison between the two boroughs who started this intervention and the others, is therefore set to the end of 2019, before the 13 others began their systematic coordination of care.

Statistical Analysis Plan

The investigators will use a controlled before and after study design to evaluate this intervention.

The cohort

All elderly 65 age or older in Oslo are included in Oslo Fall Cohort with registry data from Statistics Norway, the National Population Registry, Norwegian Patient Registry (NPR), and the Electronic Patient Records for the health services in the local municipalities. Data is available on all participants from 2010 and the investigators will start following them from January 2012 until December 2019 with the intervention starting as specified in the timeline (see above). The study will follow each cohort participants prospectively and analyze the data by Cox proportional hazards regression or similar.

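### The main analysis relies on the 2012-2013 borough difference being stable, but the plan never checks this, although untreated follow-up after 2013 is already held

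*Combined protocol and SAP*

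**What the plan says.** **Why the boroughs started.** Under needs assessment and user involvement, the protocol says: "The intervention started with the chief medical officers in the areas of intervention realizing the health burden of hip fractures within their boroughs". The sentence adds a second reason: "as well as the lack of care coordination in the delivery of preventive measures". No rate, year or comparison with other boroughs is given.

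**Main analysis.** Fallers in Nordstrand and Østensjø are compared with fallers in the 13 other boroughs over 2015-2019. For the period before, the plan says: "A similar analysis will be performed before the intervention started using data from 2012-2013". It continues: "Any differences between the intervention and control boroughs before the intervention started will be taken into account". No model or method for this is named.

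**Time trends.** The only mention is in the paragraph on the secondary analysis of total hip fracture incidence: "Adjustment for possible time trends will be considered".

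**Time available before the start.** The cohort section says: "Data is available on all participants from 2010 and the investigators will start following them from January 2012 until December 2019". The Timeline gives "Start of intervention in Nordstrand borough is set to January 1, 2015" and "Start of intervention in Østensjø borough is set to September 1, 2016". Nordstrand is therefore followed and untreated through 2014, and Østensjø through August 2016. Both stretches lie partly outside the stated before-window.

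**The concern.** A controlled before-and-after comparison can be attributed to the programme only if the gap between the two groups of boroughs would otherwise have stayed the same. Here the gap is measured once, over two years, and the plan does not look at whether it was moving. That applies to all three primary outcomes.

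For hip fracture there is a further reason to look. The boroughs chose to start, and recognising their hip fracture burden was part of the reason. If that recognition partly reflected a chance-high count in 2012-2013, the gap would have narrowed without any programme, and taking account of the 2012-2013 gap would turn the narrowing into an apparent reduction after 2015. A single window cannot separate a lasting difference from a temporary one.

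**Working it through.** **1. The plan's own figure.** Inputs from the statistical power section: 607 hip fractures, 22% exposed, RR 0.76, alpha 0.05 (two-sided assumed). By Schoenfeld's formula:
- sqrt(607 x 0.22 x 0.78) = 10.21, and |ln 0.76| = 0.274
- 10.21 x 0.274 - 1.96 = 0.84, so power is 80.0%
- events needed are 608, against the stated 607

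The stated power reproduces. It refers to the 2015-2019 contrast alone, whose log hazard ratio has SE 1/10.21 = 0.098.

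**2. Precision of the before-period ratio.** The documents give no before-period count. Assumption: E = 607 x 2/5 = 243 fractures among fallers in 2012-2013, with the same 22% share. SE = 1/sqrt(E x 0.22 x 0.78).

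| E (assumed) | SE of log HR | Corrected HR if a one-SE chance excess vanishes, no effect |
|---|---|---|
| 150 | 0.197 | exp(-0.197) = 0.82 |
| 243 | 0.155 | exp(-0.155) = 0.86 |
| 364 | 0.127 | exp(-0.127) = 0.88 |

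A half-SE excess at E = 243 gives exp(-0.077) = 0.93. On the log scale, the one-SE case is 0.155/0.274 = 56% of the design effect.

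**3. Dependence on how the boroughs came to start.** Suppose the true ratio is 1 in both periods, and the boroughs start when a trigger is above its average. Let that trigger have correlation rho with the chance error in the 2012-2013 ratio. The mean corrected log HR is -rho x SE x sqrt(2/pi). At E = 243:

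| rho | Average corrected HR, no effect |
|---|---|
| 0 | 1.00 |
| 0.25 | 0.97 |
| 0.5 | 0.94 |
| 0.75 | 0.91 |
| 1 | 0.88 |

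A simulation of one million draws agrees. The documents give no information on rho.

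**4. Carrying the before-period error through.** If the before-period log ratio is subtracted, SE = sqrt(0.155² + 0.098²) = 0.183. Power at RR 0.76 is then Phi(0.274/0.183 - 1.96) = 32% (18% to 36% for 100 to 300 before-period fractures).

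**5. What a placebo period could show.** Take a false start of 1 January 2014, E = 243 (121.5 a year), and intervention events split equally between the boroughs (11% each, an assumption).
- Intervention fractures: 0.11 x 121.5 x (12 + 32)/12 = 49
- Control fractures to August 2016: 0.78 x 121.5 x 32/12 = 253
- SE of the placebo-period log HR: sqrt(1/49 + 1/253) = 0.156
- SE after the 2012-2013 correction: sqrt(0.156² + 0.155²) = 0.22 (0.28 to 0.18 for E = 150 to 364)

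With no regression to the mean, the corrected placebo HR would still be at or below 0.86 with probability Phi(-0.151/0.22), about 25%, and at or below 0.76 about 11% of the time.

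**The case against.** A reader might infer that the plan corrects for the 2012-2013 difference as if it were permanent, and that the boroughs were in effect selected at a peak, so that a spurious benefit is to be expected. The documents do not support that.

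- The plan says only that earlier differences will be taken into account. A constant offset is the natural reading of a single window, but it is an inference.
- Regression to the mean needs selection on an unusually high value. Realising a burden is not evidence of a high, rising or recent peak, and lack of coordination is a second stated motive. For Østensjø, the Timeline ties the start to a grant being awarded.
- The window ends 12 months before Nordstrand's start and 32 months before Østensjø's. A spike just before either start would fall outside it, which weakens the mechanism.
- The motive concerned burden in the boroughs, while the main analysis is among fallers. A large burden can come from many older residents or many falls, without a high hazard after a fall.
- The motive concerned hip fracture and gives no such argument for nursing home admission or death.

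All of this stands, and it reduces regression to the mean from a demonstrated flaw to a possible one. It does not answer the main point: the design relies on a stable difference, the plan does not examine it, and the data to do so are already in the cohort.

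It is also tempting to let the placebo result decide attribution, or to dismiss any effect that appears only after correction. Neither rule is sound. Step 5 shows how often the placebo would look like a reduction by chance. And with a lasting baseline ratio of, say, 1.30 and a true effect of 0.76, the uncorrected ratio is 1.30 x 0.76 = 0.99, so the second rule would discard a correct result.

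**Conclusion.** The concern holds in a limited form. The main comparison takes account of a difference measured only in 2012-2013, in boroughs that chose to start. The plan contains no check that this difference was stable, and time-trend adjustment is optional and confined to the secondary analysis.

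Regression to the mean could produce a corrected hazard ratio of about 0.86 with no effect, if a one-SE chance excess in 2012-2013 vanished and E = 243. The bias is zero if the start did not track such an excess. The size therefore rests on an assumed event count, the 22% share carried back to 2012-2013, and an unknown link between the decision to start and chance. The documents establish neither the link nor the count.

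The stated 80% power is correct for the uncorrected contrast but does not cover a baseline-corrected one. This is a worthwhile and inexpensive improvement, not a fault that invalidates the design.

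**What to change.** Add to the main analysis in the SAP, before results are seen:

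1. **Pre-start hazard ratios.** Using untreated follow-up (Nordstrand 2012-2014, Østensjø January 2012 to August 2016), report the intervention/control hazard ratio among fallers by pre-start period and by borough, with confidence intervals.
2. **A placebo-period contrast.** Apply the same model and the same 2012-2013 correction with a false start of 1 January 2014, on Nordstrand in 2014 and Østensjø from January 2014 to August 2016, against concurrent control fallers. Report it as an estimate with its interval. It shares the 2012-2013 baseline with the main estimate, so a chance excess there would push both below 1.
3. **Uncorrected and corrected results together.** Show the 2015-2019 hazard ratio both ways. State the adjustment model, for example a borough-group by period interaction, so that the error of the before-period estimate is carried into the interval.
4. **Use.** State that these results inform interpretation and are not a pass/fail rule for attributing an effect to the programme.

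The cost is a few more runs on data already held, plus SAP wording. The downsides are an imprecise placebo estimate (log-HR SE about 0.22 under the assumptions above), a wider interval for the corrected result, and possibly a more cautious conclusion.

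### The SAP does not say how the 2012–2013 borough difference enters the effect estimate, or whether it always does, and its 80% power is for the uncorrected contrast

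*Combined protocol and SAP*

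**What the plan says.** The Statistical Analysis Plan opens with the design: "The investigators will use a controlled before and after study design to evaluate this intervention". Under The cohort, the method is to "analyze the data by Cox proportional hazards regression or similar".

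The Main analysis paragraph then sets three things side by side:

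- The main contrast is confined to the later window: "In the main analysis (2015-2019), fallers from the two intervention boroughs" are compared with fallers from the control boroughs.
- The earlier window is a second, separate exercise: "A similar analysis will be performed before the intervention started using data from 2012-2013".
- The connection between them is: "Any differences between the intervention and control boroughs before the intervention started will be taken into account".

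No borough-by-period term, ratio of hazard ratios, joint model or definition of a difference is given. Adjustment for time trends is only to be considered, and that remark belongs to the secondary analysis.

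The Statistical power section assumes 22% of fallers exposed and 607 hip fractures among fallers over 2015–2019, and concludes that "it will enable us to detect a relative risk reduction of 24% (RR= 0.76" with 80% power at the 0.05 level. It gives no event count for 2012–2013.

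**The concern.** Two boroughs are compared with thirteen others, without randomisation. A stable difference in hip-fracture risk among their fallers, present before any programme, is plausible. The before-period contrast is the part of the design that separates such a difference from a programme effect.

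The linking sentence allows two procedures. Under one, the before-period log hazard ratio is always subtracted from the after-period one. Under the other, the analyst looks at 2012–2013, judges whether a difference is there, and corrects only if it is. The second is a preliminary test with a short window behind it. It keeps the uncorrected estimate in most cases where a modest real difference exists, and the final test then does not hold its nominal 5%.

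The error can go either way. A stable advantage in the intervention boroughs can look like benefit; a stable disadvantage can hide a real benefit or look like harm. Separately, readers may take the 80% power as describing the before-after estimate, which it does not.

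**Working it through.** **1. The plan's own figure.** For a single two-group hazard comparison, the events needed are D = (z₀.₉₇₅ + z₀.₈₀)² / [p(1−p)(ln RR)²]. With p = 0.22 and RR = 0.76 this is 7.849 / (0.1716 × 0.0753) = 607.3. The stated 607 events and 80% power therefore reproduce, two-sided (a one-sided test would need 479). The formula holds only the 2015–2019 contrast and makes no allowance for subtracting a before-period estimate.

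**2. Before-period events (assumed).**
- Central: 607 × 24/60 = 243, a constant yearly rate.
- Low: 607 × (2/5)² = 97, because everyone starts as a non-faller and faller time builds up from zero in each window.
- High: 304, about half of 607, a generous upper case.

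**3. Standard errors of the log HR, 243 before-period events.**
- After, staggered start: control events 607 × 0.78 = 473.5. Intervention events 607 × 0.22 = 133.5, assumed split equally (66.8 per borough). Østensjø is exposed for 40 of 60 months, so exposed events are 66.8 + 66.8 × 40/60 = 111.3. SE = √(1/473.5 + 1/111.3) = 0.1053.
- After, 22% exposed throughout as in the plan's calculation: SE = 1/√(607 × 0.1716) = 0.0980.
- Before: 243 × 0.22 = 53.5 and 243 × 0.78 = 189.5. SE = √(1/53.5 + 1/189.5) = 0.1549.
- After minus before: √(0.1053² + 0.1549²) = 0.1873 (staggered), or √(0.0980² + 0.1549²) = 0.1833 (22% throughout).

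**4. False-positive rates with no programme effect and a stable log-HR difference δ.** The illustrative conditional rule uses after minus before if |before estimate|/0.1549 > 1.96, and otherwise the after estimate alone. Its rates come from simulating at least 1,000,000 pairs of independent normal estimates. Columns 2 and 3 are Φ(−1.96 + δ/SE) + Φ(−1.96 − δ/SE), with SE 0.1549 and 0.1053. Staggered start; rejections in both directions are counted.

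| δ | Before analysis reaches p<0.05 | Never corrected | Corrected only at p<0.05 | Always corrected |
|---|---|---|---|---|
| 0 | 5% | 5% | 7% | 5% |
| 0.05 | 6% | 8% | 10% | 5% |
| 0.10 | 10% | 16% | 17% | 5% |
| 0.15 | 16% | 30% | 27% | 5% |

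Over this range the conditional rule protects little better than no correction. At δ = 0.10 its rate stays at 16–18% for 97 to 300 before-period events. With 22% exposed throughout and 243 events, the rate is 19% at a stable HR of 0.90 and 34% at 0.85.

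**5. Power of the before-after estimate at RR 0.76** (|ln 0.76| = 0.2744). Power = Φ(0.2744/SE − 1.96); detectable RR at 80% power = exp(−2.802 × SE).

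| Before-period events | SE | Power | Detectable RR |
|---|---|---|---|
| 243, staggered | 0.187 | 31% | 0.59 |
| 243, 22% throughout | 0.183 | 32% | 0.60 |
| 97, 22% throughout | 0.264 | 18% | 0.48 |
| 304, 22% throughout | 0.170 | 37% | 0.62 |

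The matching uncorrected powers are 80% with 22% throughout, and Φ(0.2744/0.1053 − 1.96) = 74% with the staggered start.

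**The case against.** The strongest reply is that the plan contains no preliminary test. The sentence names no p-value or threshold, its wording reads naturally as a commitment to correct in every case, and the declared design points the same way. Separate windows do not imply a trigger, since after divided by before can be formed from two separately fitted hazard ratios. A power figure for the later contrast says nothing about when a correction applies. All of this stands. A reader might infer that the SAP prescribes correction only after a significant before-period difference; the documents do not say so, and under unconditional correction the excess error is zero.

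Two other strong inferences also fail:

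- That a stable difference missed in 2012–2013 would be reported as a programme effect. Even under the assumed rule, differences of 0.05 to 0.15 lead to rejection in 10–27% of cases, so most do not.
- That the choice has been shaped by results already seen. The plan is dated January 2023 and follow-up ended in December 2019, but Data management and analysis states that nothing relating the programme to outcomes was analysed before registration. What remains is ordinary discretion: both windows will be available at analysis with no rule fixed.

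The 5% for constant correction is itself conditional. It needs independent individuals and no differential trend between borough groups, which two treated boroughs cannot guarantee.

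None of this supplies the missing estimator. If unconditional correction is intended, saying so costs no precision beyond what is already planned, and the power statement still describes a different quantity.

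**Conclusion.** The concern holds as an unspecified correction. The plan permits, but does not prescribe, reporting the uncorrected 2015–2019 hazard ratio when the before-period difference looks small or non-significant. The possible inflation runs from none (always corrected) to about 7%, 17% and 27% at stable log-HR differences of 0, 0.10 and 0.15. The upper figures rest on an assumed p<0.05 rule, an assumed 243 before-period events and an equal split of intervention events between the two boroughs.

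The power point does not depend on which reading is right. The 80% is arithmetically correct for the uncorrected contrast. The before-after estimate has about 31–32% power at RR 0.76 and a detectable RR of about 0.6 with 243 before-period events. Both sets of figures treat individuals as independent, so real precision may be lower. The change should be made, because it concerns the comparison that defines the design.

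**What to change.** Replace the linking sentence in Main analysis with:

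> The effect estimate is the intervention-by-period term (after hazard ratio divided by before hazard ratio) from one model covering both windows. It is retained whatever the size or p-value of the before-period difference. The 2015–2019 hazard ratio alone is descriptive.

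In Statistical power, state that 80% at RR 0.76 refers to the uncorrected 2015–2019 contrast, and add the figure for the before-after estimate using the actual 2012–2013 event count. Until that count is inserted, the working figures are about 31–32% power and a detectable RR of about 0.6 at 243 events, with power of about 18–37% over 97–304 events.

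The cost is a replaced SAP passage, one combined model and a rewritten power paragraph. The real price is a wider interval (SE of the log HR about 0.19 against 0.10) and a less favourable power statement. That width is the uncertainty of a before-after estimate; the narrower interval is valid only if the boroughs had no baseline difference.
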